## 6.5 POOLING OF CENTRES

There is no analysis planned by centre due to the small number of patients to be recruited per centre.

## 6.6 HANDLING OF MISSING DATA AND OUTLIERS

Based on the different reasons of patients' data missing for different endpoints, various methods will be used to assess the impact of missing data on the efficacy endpoints of this trial, depending upon the type of the endpoint.

### 6.6.1 Methods of data selection

#### Original results (OR) analysis

Original result analysis implies the analysis of data exactly as observed. OR analysis will be performed on endpoints where it is not meaningful to apply any imputation rule on them for replacing missing values.

#### Observed cases (OC) analysis

OC analyses only use the available data that were observed while patients were on-treatment. Any values collected after treatment discontinuation and any values collected after the start of rescue medication will be set to missing.

#### Observed cases – Rescue observed cases (OC-ROC) analysis

Only the available data that were observed while patients were on-treatment will be considered. Any values taken after rescue medication intake will be kept. Any values collected after treatment discontinuation will be set to missing.

#### Observed cases – Last observation carry forward (OC-LOCF) analysis

Based on the OC data, the post-baseline missing values, post-treatment values and values after rescue medication will be imputed by the last on-treatment observation without rescue medication carried forward. In case, there is no on-treatment observation without rescue medication, baseline value will be carried forward.

#### Observed cases - all data (OC-AD) analysis

All available data that were observed are considered. Any values taken after the start of rescue medication and any on- and post-treatment values will be kept.

#### Observed cases - all data and baseline observation carry forward (OC-AD-BOCF) analysis

Based on the OC-AD data, baseline observation will be carried forward to impute the missing data.

#### Non-completers considered failure (NCF)

For binary endpoints, like the occurrence of a response, a conservative method to replace missing values is to consider them as "failures". Post-treatment values will be set to missing. Missing data due to early discontinuation of treatment and values after the start of rescue

medication will be replaced as "failure" (e.g. non-responder) up to the planned time point for the analysis.

For binary endpoints that are derived from quantitative endpoints (e.g. HbA1c) missing on-treatment data at the planned time point for the analysis will be replaced by NCF.

### 6.6.2 Imputation methods

A multiple imputations (MI) approach will be considered to impute missing data. Multiple imputation approaches taken are specified in [Section 7](#) within the planned analyses.

Missing safety data will not be replaced.

### 6.6.3 Missing dates and times

Missing or incomplete AE dates are imputed according to BI standards (see “Handling of missing and incomplete AE dates”) ([3](#)).

Missing data and outliers of PK data are handled according to ([2](#)).

If the date of first drug administration is missing but the patient was randomised, the date of the first drug administration will be set to the date of randomisation. If the date of first administration is partially missing with the month and year present, the day will be set to the date of randomisation if randomisation was in the same month. If randomisation was in the month prior to the first drug administration the missing day will be imputed as the first day of the month.

A missing time of first drug administration will be imputed as 08:00 o'clock in the morning, missing administration times at on-treatment visits will be imputed by 08:00 o'clock in the morning.

The earliest of the listed dates will be picked to impute the missing or incomplete drug stop date:

- Date of End of Treatment (EOT) visit (either premature treatment discontinuation visit date or Visit 8 / EOT)
- Last contact date recorded in the EOS page
- Date of death
- Imputation of partial last date of study medication (imputed as last day of the month if only day is missing / last day of year if only year is provided)

For partial start and stop dates for concomitant therapies the following derivations will be used to impute 'worst case' values:

- If the day of the end date is missing then the end date is set to last day of the month.
- If the day and month of the end date are missing then end date is set to 31st December of the year.
- If the day of the start date is missing the start date is set to first day of the month.

- If the day and month of the start date are missing then the start date is set to 1st January of the year.

For other incomplete date information (except to assess the overall compliance, see below) always the midpoint of the possible interval will be used. If only the year is present the day and month will be imputed as 01 July, if year and month is present the day will be imputed as 15. If the year is missing, the date will be considered missing.

All other cases need to be assessed by the trial team on an individual basis, using the above points as guidance.

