6.1 VISIT SCHEDULE

Trial visits should start between 7.00 AM and 11.00 AM and ideally should be scheduled as early as possible when overnight fast is required (at least 8 hours with no food or drink and water only).

Smoking is not permitted prior to or during any of the visits (this includes from the start of the overnight fast that precedes all visits). Excessive food and alcohol intake should be avoided in the 2 days prior to each visit.

All patients are to adhere to the visit schedule as specified in the [Flow Chart](#). Some flexibility is allowed in scheduling the visits according to the visit time windows as specified. The trial medication kits will contain sufficient medication to allow for these protocol-permitted visit windows. All deviations from the planned visit schedule will be documented. If any visit has to be re-scheduled, subsequent visits should follow the original visit schedule (calculated from Visit 2).

If a patient mistakenly takes trial medication in the morning of a visit where blood samples are drawn for PK assessment or comes in non-fasted where a fasting condition is required, the visit should be re-scheduled to the next day reminding the patient about the expected conditions.

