6.2.2 Treatment period(s)

For patients eligible to be randomised, assessments should be performed as mentioned in the [Flow Chart](#) and the respective protocol sections.

Visits 2, 5 and 8 have to be performed in a fasted state (overnight fast for at least 8 hours, no food intake, only water allowed).

Initial randomisation at Visit 2

Eligible patients will be randomised by using the IRT system; all visit assessments should have been completed prior to this, and before the first intake of study medication. First dose of trial drugs will be administered in the clinic (Day 1).

Starting from Visit 2, the SBGM/CGM/SBKM device will also be used by the patient to measure his/her blood glucose concentration and blood ketone concentration before breakfast. He/she or his/her parents/legal guardian should enter the values in the patient diary. Those values will then be reviewed by the investigator or delegated site personnel at each clinic visit. In order to make sure those measurements are well performed, the investigator or a delegated site staff representative should contact the patient or the parent/legal guardian by phone/text message/email a day or two after randomised treatment is started and then after 2, 8, 18, 22, 34, 38, 46 and 50 weeks of treatment.

These measurements should be performed as described in the [Flow Chart](#) and in [Section 5.3.5.2](#) and [5.3.5.3](#).

Next clinic visits will be scheduled after 4, 12, 14, 26, 30, 42 and 52 weeks of treatment (Visit 3 to 8). For detailed description of the trial procedures at each visit and dispensing schedule, please refer to the Flow Chart.

Re-randomisation at Visit 4B (Week 14)

Patients not achieving an HbA1c value < 7.0% at Visit 4A (as measured by the central laboratory) and initially randomised to empagliflozin 10 mg will be re-randomised to receive either empagliflozin 10 mg or empagliflozin 25 mg. In order to maintain the blinding, an IRT call will be performed for all patients. Medication numbers will be assigned through the IRT system based on the HbA1c value at Visit 4A and the age at baseline.

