#### 6.7 BASELINE, TIME WINDOW, AND CALCULATED VISITS

The term “baseline” refers to the following definitions according to the individual analysis period.

- *Study baseline*: Last observed measurement prior to administration of any initially randomised study medication at Day 1.
- *Titration baseline*: Last observed measurement prior to administration of the re-randomised study medication for the initial empagliflozin patients at Week 14. If last observed measurement is after rescue medication then there is no titration baseline for OC analysis.
- *Safety extension baseline*: Last observed measurement prior to administration of the re-randomised study medication for the initial placebo patients at Week 26.

Note: On or prior to date of randomisation will be used, instead of prior to date of drug administration, for randomised patients who have not taken any blinded study drug.

Both date and time of administration of the randomised study medication are expected to be recorded at Day 1, Week 14 and Week 26. In the determination of baseline for a parameter, if the parameter of interest:

- is collected with date and time: both date and time are used in the calculation of ‘last observed measurement prior to administration’. If the dates and times are equal, the parameter will be determined to be prior to administration.

- is collected with only date: the dates are equal, the parameter will be determined to be prior to administration.

The exception to this rule, is HbA1c, whereby even though time of sample is collected, it will be handled as if it was collected only with date.

Measurements taken after the first intake of randomised study drug will be considered on-treatment values if they have been obtained up to the end of the endpoint specific follow-up period as defined in [Table 6.7: 1](#).

Table 6.7: 1 Endpoint specific follow-up period for the assignment to treatment phase

Endpoint	Last day of assignment to treatment phase (days after study drug stop date)
Efficacy	
HbA1c	7
FPG	1
Body weight	1
BMI z-score	1
Blood pressure (systolic, diastolic)	1
UACR	7
Safety	
Adverse events	7
AESI Hepatic injury 	30
AESI Lower limb amputation	End of study
Safety laboratory measurements	7
AST/ALT/TBILI 	30
Pulse rate	1
C-peptide	1
Tanner staging	1

[1] Refers to a specific safety analysis including all hepatic injuries with an onset date up to 30 days after the study treatment stop.

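### A missing Day 1 dosing time set to 08:00 turns later pre-dose samples into post-dose ones and can remove the baseline for FPG and some laboratory markers (minor)

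*SAP*

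**What the plan says.** SAP 6.6.3 gives the fallback for a missing clock time: "A missing time of first drug administration will be imputed as 08:00 o'clock in the morning". The same sentence applies 08:00 to missing administration times at on-treatment visits.

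SAP 6.7 defines study baseline as the last measurement before the first randomised dose. If a parameter "is collected with date and time: both date and time are used in the calculation of" whether it came before the dose. Ties go to baseline: "If the dates and times are equal, the parameter will be determined to be prior to administration". A parameter with only a date counts as pre-dose when the dates agree. One analyte is exempt: for HbA1c, "even though time of sample is collected, it will be handled as if it was collected only with date".

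The protocol fixes the order of events. Under Section 6.1, "Trial visits should start between 7.00 AM and 11.00 AM". Under Section 6.2.2, before randomisation at Visit 2, "all visit assessments should have been completed prior to this, and before the first intake of study medication"; the first dose is then given in the clinic. Section 5.2.1 places the FPG sample before trial medication, and Section 6.2 places blood pressure, pulse and ECG before any blood draw.

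**The concern.** The fallback time lies one hour into a four-hour range of visit starts, and dosing comes last in the visit. In most cases 08:00 will therefore be earlier than the true dosing time, and often earlier than the blood draw. The protocol order shows that the sample is pre-dose; the imputed clock says the reverse, and SAP 6.7 follows the clock.

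At stake is the FPG change from baseline in the affected patients. SAP 7.5.2.1 uses baseline FPG both in the change score and as a covariate. Without it a patient with a valid Week 26 value drops out of both FPG approaches. Baseline carried forward cannot help, because there is no baseline to carry. Changes in growth and bone markers, which are safety endpoints, would be lost in the same way.

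**Working it through.** The documents give no figure for this point, so there is none to reproduce. The check applies the SAP rules to samples that are truly pre-dose.

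**Step 1: the rule.** A timed sample is eligible as baseline if sample time ≤ dosing time. With dosing imputed at 08:00:
- 07:30 and 08:00: baseline
- 08:01 and 09:15: post-dose

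**Step 2: what happens to the rejected value.** Footnote B of SAP Table 6.7: 2 allows only values taken before the start of treatment to serve as study baseline. The first post-baseline window (Week 4) opens on Day 2. The Day 1 value can be neither baseline nor follow-up.

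**Step 3: is there an earlier value?** From the protocol Flow Chart with its footnote 7, and Sections 5.3.3 and 5.3.5.4:
- FPG is drawn at Visits 2, 5 and 8 only, so there is no earlier value.
- IGF-1, IGF-BP3, PINP, NTx, intact PTH, 25-OH-vitamin D, calcium and phosphate are first drawn at Visit 2 and are not in the Visit 1A panel, so there is no earlier value.
- C-peptide, creatinine and alkaline phosphatase are also measured at Visit 1A, where fasting is not required. Read literally, the SAP replaces the Visit 2 baseline with the screening value.

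The SAP writes an explicit fallback to screening only for HbA1c.

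**Step 4: share of draws misclassified when the dosing time is missing.** Assumptions, not in the documents: visit starts uniform from 07:00 to hour E, and blood drawn d hours after the start. For E + d > 8 and d ≤ 1, the share drawn after 08:00 is (E − (8 − d)) / (E − 7).
- E = 11, d = 0: 3/4 = 75%
- E = 11, d = 0.5: 3.5/4 = 87.5%
- E = 11, d = 1: 4/4 = 100%
- E = 9, d = 0: 1/2 = 50%
- E = 9, d = 0.5: 1.5/2 = 75%

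If every visit started by 08:00, the share would be 0% with no delay and 50% with a half-hour delay.

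**Step 5: patients.** Expected FPG baselines lost = 150 × assumed missing rate × share, with the share from 50% to 100%:
- 1% missing: 150 × 0.01 = 1.5, so 0.75 to 1.5
- 5% missing: 150 × 0.05 = 7.5, so 3.75 to 7.5

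**Step 6: under the HbA1c rule.** Comparing by date only makes every same-day sample at Visit 2 pre-dose. The share misclassified becomes 0% whatever the draw time.

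**The case against.** The strongest objection is that two conditions must coincide. First, the dosing time must be missing, yet SAP 6.7 says: "Both date and time of administration of the randomised study medication are expected to be recorded at Day 1, Week 14 and Week 26". Second, the sample must carry a clock time, which the SAP states only for HbA1c. If the other analytes carry a date only, the date rule makes same-day samples pre-dose and nothing goes wrong. Both points stand, and they limit how often the problem can occur. They do not make the fallback right when it is used.

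It is also fair that Protocol 6.1 asks for fasting visits as early as possible, so starts spread evenly up to 11:00 may be too late. This is why the range above reaches down to 50%.

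A reader might infer more than the documents support:
- **That the C-peptide baseline and all bone-marker baselines disappear.** C-peptide and alkaline phosphatase have Visit 1A values. Their baselines would be replaced. For C-peptide this still matters, because SAP 7.1.1 tabulates the fasting value.
- **That the Week 26 safety extension baseline of placebo patients is removed.** They have earlier values from Visit 2 onwards, so the baseline would fall back to an older one. A missing time is also less likely there: Protocol 5.4.1 requires exact dosing and sampling times at Visit 5. The FPG, IGF and bone-marker analyses in the available SAP text do not rely on that baseline.
- **That DPP-4 is affected.** SAP 7.8.2.5 summarises the Day 1 pre-dose measurement itself, with no change from baseline.
- **That the confirmatory result is at risk.** HbA1c is compared by date, and FPG lies outside the tested hierarchy.

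**Conclusion.** The rule as written gives the wrong label. When the Day 1 dosing time is missing, a protocol-compliant pre-dose sample with a recorded time after 08:00 is called post-dose. The patient then has no baseline for FPG, IGF-1, IGF-BP3, PINP, NTx, PTH, 25-OH-vitamin D, calcium and phosphate. Fasting C-peptide, creatinine and alkaline phosphatase silently take a screening value.

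The point is minor. It depends on sample times being recorded for these analytes, which is likely but not stated, and on missing dosing times, for which no rate is given. The counts of about 1 of 150 at 1% missing and 4 to 8 at 5% are illustrations that rest on assumed missing rates and visit times.

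**What to change.** Add one sentence to SAP 6.7, next to the HbA1c exception: *When the dosing time at a visit is missing or has been imputed, samples that the protocol schedules before dosing at that visit are compared with dosing by date only.* SAP 6.6.3 can keep 08:00 for other uses, with a cross-reference to this sentence.

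The cost is one sentence and a small change to the baseline derivation program. No new data are needed. The sponsor can also tabulate how many Day 1 and Week 26 dosing times are missing, which would settle whether the rule was ever used.

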4.2 OTHER TREATMENTS, EMERGENCY PROCEDURES, RESTRICTIONS

4.2.1 Other treatments and emergency procedures

Background therapy

Throughout the duration of the trial, patients should continue to take their background therapy (metformin and/or insulin). The dose of background therapy at the time of screening will be recorded in the source documentation and on the appropriate pages of the eCRF. If medically appropriate, the dose and dosing frequency should then remain unchanged. For patients on insulin, the weekly average variation of the basal insulin dose should remain ≤ 0.1 IU/kg.

Background therapies will not be provided by BI as part of the clinical trial supplies, unless required by local laws and regulations.

For patients on insulin, investigators are advised to adjust the patient's total insulin dose based on need as assessed by frequent SBGM and close patient follow-up upon initiation of randomised trial medication. In all cases, the actual reduction will be dependent upon individual glucose values. Thereafter and until the end of the trial, further adjustments to insulin therapy (both basal and, MDI insulin) may be implemented as necessary to avoid hypoglycaemia and also hyperglycaemia to ensure that, in the investigator's opinion, the patient is achieving the best standard of care in accordance with local guidelines. In addition,

transfers to another type or brand of insulin as well as changes of the type of insulin pen should be avoided.

For patients on metformin, in case a vascular administration of iodine containing contrast agent is required, metformin should be temporarily discontinued as specified in the SmPC.

Rescue medication

The use of rescue medication will be permitted in this trial and will be metformin and/or insulin. The use of rescue medication will be permitted from the first day of treatment (after randomisation) until the end of the trial.

DINAMO™

Rescue medication (insulin or increased doses of insulin) should be initiated:

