1. from the first day of treatment (after randomisation) until Week 52 in case of acute metabolic decompensation accompanied by significant symptoms (e.g., vomiting, dehydration, lethargy) and/or repeatedly elevated blood ketone (beta hydroxybutyrate) values > 1.5 mmol/L measured with the provided electronic device (meter), irrespective of the glucose value (due to its mechanism of action, empagliflozin may potentially modify the clinical presentation of acute metabolic decompensation, e.g. with lower blood glucose values than expected).

However, in case of sustained hyperglycaemia during SBGM (80% of blood glucose tests are > 300mg/dL (16.6 mmol/L) (non-fasting) or > 200 mg/dL (11.1 mmol/L) (fasting) for 1 week) initiation of rescue therapy should also be considered.

2. from Week 12 (Visit 4A) until Week 52 (Visit 8) if on two successive occasions (separated by at least 4 weeks) HbA1c is $\geq 9.0\%$ and an absolute increase of HbA1c $\geq 1\%$ compared with the baseline value is observed (even in the absence of symptoms related to hyperglycaemia and ketoacidosis).

The type of insulin and its dosage will be left at the investigator's discretion.

If new insulin treatment or insulin treatment at increased doses (i.e. dose increase of basal insulin of more than 0.1 IU/kg above the baseline prescribed dose) continues for more than 21 consecutive days (including the weaning phase) then the patient will be classified as requiring rescue therapy.

DINAMO™ Mono

Rescue medication (metformin and/or insulin) should be initiated:

- at anytime in case of acute metabolic decompensation;
- if HbA1c > 7.0% **AND**
 - o there is no HbA1c decrease at Week 12
 - o the HbA1c decrease is less than 0.5% at Week 26 and later

In addition, rescue medication could be initiated at any time as per the investigator's judgement. The type of insulin and its dosage as well as the dosage of metformin will be left at the investigator's discretion.

On top of the HbA1c measurements performed at the time points defined in the [Flowchart](#), additional HbA1c measurements can be performed at any time if deemed necessary by the investigator. Besides, additional interactions (e.g. phone calls, text messaging or emails, as deemed appropriate by the investigator and the patient) must be planned every 4 weeks between 2 visits where the interval exceeds 4 weeks.

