Furthermore, some patients may require use of insulin due to temporary medical conditions such as hospitalisation or intercurrent illness. Any type or dose of insulin can be used at the discretion of the investigator. In such cases, an attempt is made to withdraw insulin once the acute event has resolved. In the case of a temporary medical condition such as hospitalisation or intercurrent illness, weaning occurs within 2 weeks if the event lasted 2 weeks or less; if the event lasted more than 2 weeks, weaning occurs within 1 month. Withdrawal of insulin occurs regardless of blood glucose values; if metabolic decompensation occurs, appropriate safety procedures are followed as detailed in [Section 5.3.5.3](#).

In the case of hypoglycaemia that may put patient on risk (e.g. repeated symptomatic hypoglycaemia or severe hypoglycaemia), appropriate adjustment of oral antidiabetic therapy and/or insulin therapy such as a dose reduction / discontinuation of ongoing rescue medication or existing background therapy should be initiated. Reduction or discontinuation of ongoing rescue medication should be considered before a reduction in the dose of existing background therapy.

Any rescue medication or dose change in background therapy will be recorded in the source documents and on the appropriate pages of the eCRF.

Any additional treatment that does not qualify as a rescue medication and is considered as deemed necessary for the patient's welfare may be given at the investigator's discretion. Exceptions to this are the restrictions described in section 4.2.2.1.

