#### DINAMO Mono

The primary efficacy endpoint is the occurrence of treatment failure up to or at Week 26 as a binary endpoint. Treatment failure is defined as meeting at least one of the following criteria:

- Use of rescue medication, see [Section 7.6.1](#), at any time up to Week 26 (including Week 26)
- Increase from baseline in HbA1c by 0.5% (at least 0.5% in absolute value) at Week 26
- Increase from baseline in HbA1c to above 7.0% at Week 26 in patients with baseline HbA1c < 7.0%

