## 7.2 CONCOMITANT DISEASES AND MEDICATION

Only descriptive statistics are planned for this section of the report using the TS and TSactive accordingly.

Concomitant therapy use will be summarised by Anatomical-Therapeutic-Chemical classification level 3 (ATC3) and preferred name. Only therapies under their available ATC3 code(s) will be presented. Summaries will be presented for concomitant therapies taken during randomised treatment which are newly initiated (i.e. new preferred name) during the dedicated randomised treatment period and those taken at baseline (i.e. on day 1) of the dedicated randomised treatment period.

The summary on concomitant therapies during randomised treatment will be presented up to Week 26 by treatment grouping 1 and Week 52 by treatment grouping 6.

Separate summary of use of antihypertensives, ASA, or lipid lowering drugs at baseline will be presented by TG1 and during randomised treatment will be presented up to Week 26 by treatment grouping 1 and Week 52 by treatment grouping 6. The displayed categories and defining ATC levels and ATC codes are shown in [Section 9.2](#).

Concomitant diagnoses and non-drug therapies at any time of the study will be summarised by Medical Dictionary for Regulatory Activities (MedDRA) System Organ Class (SOC) and preferred term (PT). Relevant diabetic medical history will also be presented by treatment grouping 1.

Background antidiabetic treatment at baseline (i.e. on day 1) will be summarised for the DINAMO patients only by treatment grouping 1 presenting number of background antidiabetic treatments (0, 1, 2), background antidiabetic treatment (metformin only, insulin only, metformin and insulin, none (diet and exercise only, metformin not tolerated)), metformin total daily dose [mg] (continuous and categories), and basal insulin total daily dose [IU/day].

Antidiabetic medication newly introduced on treatment will be presented up to Week 26 by treatment grouping 1 and Week 52 by treatment grouping 5. The increase dose of insulin during the on-treatment period is not included in this presentation for the DINAMO patients but it will be presented in the “initiate glycaemic rescue therapy” further efficacy endpoint. The antidiabetic medication newly introduced on treatment will be regarded as rescue medication for the DINAMO Mono patients.

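### Partial start dates for rescue therapy are imputed to the first of the month or 1 January with no visible floor at first dose or Visit 5, which can misclassify failure in DINAMO Mono

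*SAP*

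**What the plan says.** SAP 6.6.3 imputes partial concomitant-therapy dates to what it calls worst-case values. For starts: "If the day of the start date is missing the start date is set to first day of the month", and "If the day and month of the start date are missing then the start date is set to 1st January of the year". Stop dates go to the last day of the month or to 31 December. No bound is stated at first dose, randomisation or Visit 5. In the same section, a partial date of first study-drug intake is anchored: "the day will be set to the date of randomisation if randomisation was in the same month".

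Rescue in this trial is metformin and/or insulin. Protocol 4.2.1 states: "The use of rescue medication will be permitted from the first day of treatment (after randomisation) until the end of the trial". On recording it says: "Any rescue medication or dose change in background therapy will be recorded in the source documents and on the appropriate pages of the eCRF". SAP 7.2, the concomitant-medication section, states: "Antidiabetic medication newly introduced on treatment will be presented up to Week 26 by treatment grouping 1 and Week 52 by treatment grouping 5". It adds that in Mono such newly introduced medication is treated as rescue.

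The rescue date is used in these places:
- SAP 5.1: Mono treatment failure includes rescue up to Week 26, Week 26 itself included, with Section 7.6.1 cited for rescue.
- SAP 5.2.2: Mono time to treatment failure.
- SAP 6.6.1: the OC, OC-LOCF and NCF data selections.
- Protocol 4.2.1: in DINAMO, new or increased insulin is rescue if it "continues for more than 21 consecutive days (including the weaning phase) then the patient will be classified as requiring rescue therapy".

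**The concern.** A rule that moves a start backwards without a floor can push it across a boundary that decides an outcome. Two boundaries matter.

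**Visit 5.** In Mono, HbA1c above 7.0% with a fall of less than 0.5% at Week 26 calls for rescue (Protocol 4.2.1). HbA1c failure instead needs a rise of at least 0.5%, or crossing 7.0% from below (SAP 5.1). A patient with baseline at or above 7.0%, a Week 26 value above 7.0% and a change strictly between -0.5 and +0.5 meets the rescue criterion without being an HbA1c failure. If that patient completes treatment to Week 26 without earlier rescue, the date of the rescue prescribed on that result decides failure. Back-dated, it creates a failure. It also makes the Week 26 HbA1c a post-rescue value, which is missing in OC and replaced by an earlier value in OC-LOCF.

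**Day 1.** A start soon after first dose can be dated before it. The drug then looks like therapy already present at baseline, and a true failure can be lost.

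The shifts act in opposite directions, so the worst-case label does not describe the rule's effect consistently. Even the Visit 5 shift is unfavourable to the drug only in an active arm; in the placebo arm it favours the drug.

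**Working it through.** **1. The protocol's own intervals.** Protocol 7.7.2 tabulates exact 90% intervals for the Mono risk difference (active minus placebo). An independent Chan-Zhang calculation (two one-sided 5% exact tests, score statistic, maximised over the nuisance rate) reproduces both rows for 6 per group:
- placebo 5/6, active 1/6: -66.7 points, (-93.9, -12.4)
- placebo 5/6, active 2/6: -50.0 points, (-85.6, 5.5)

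**2. One patient.** With about 6 per arm (Protocol synopsis), one patient is 1/6 = 16.7 points.
- False failure in an active arm: 5/6 v 1/6 becomes 5/6 v 2/6, and zero enters the interval.
- True failure lost on placebo: 5/6 v 1/6 becomes 4/6 v 1/6, which also gives (-85.6, 5.5).
- False failure on placebo: 4/6 v 1/6 becomes 5/6 v 1/6, and zero leaves the interval.

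**3. How often a partial date crosses a boundary.** Assume the day is missing and the reference day is uniform over the calendar (1,461 consecutive days, mean month 1461/48 = 30.44 days). For a start d days after the reference:
- P(dated before Day 1) ≈ 1 - (d + 1)/30.44. At d = 7: 1 - 8/30.44 = 74%.
- P(dated on or before Visit 5) ≈ 1 - d/30.44. At d = 7: 1 - 7/30.44 = 77%.

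Full enumeration gives:

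| Days after reference | Before Day 1 | On or before Visit 5 |
|---|---|---|
| 1 | 93% | 97% |
| 7 | 74% | 77% |
| 14 | 51% | 54% |
| 21 | 28% | 31% |
| 28 | 5% | 8% |

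With only the year known, a start 84 days after Day 1 is dated before Day 1 in 77% of positions. A start 182 days after Visit 5 is dated on or before Visit 5 in 50%.

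**4. Example.** Day 1 is 10 March 2021, so Visit 5 (182 days later) is 8 September 2021. Rescue on 24 March with the day missing is dated 1 March, 9 days before first dose. Rescue on 20 September is dated 1 September, 7 days before Visit 5.

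**5. The 21-day insulin rule.** With both days missing, a short course becomes at least a whole month, 28 to 31 days, and always exceeds 21. With only the start day missing, courses of 3 to 14 days exceed 21 days in 56% of positions. Visit dates do not cure this: the Week 14 and Week 26 visits are 12 × 7 = 84 days apart, and a calendar month lying wholly between them is untouched by a bound at either visit.

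**The case against.** The strongest objection is that the rules for rescue may sit in text we cannot see. SAP 5.1 sends the reader to Section 7.6.1, which is withheld, so the absence of a safeguard cannot be asserted. This stands, and the point is conditional on it.

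Other limits also stand:
- No rate of partial dates is given. Concomitant therapy is reviewed at every visit and rescue is recorded in the eCRF, so partial dates may be few. All percentages above are conditional on a partial date.
- The Day 1 case removes a failure only if the newly-introduced wording of SAP 7.2 governs; the criterion in SAP 5.1 shows no lower bound. In Mono, an antidiabetic dated before Visit 2 would also conflict with exclusion criterion 7 and might be noticed. The SAP expects rescue from the first on-treatment visit, about 28 days in, where the day-missing risk is only 5%.
- Patients rescued on HbA1c (above 7.0% in Mono, at least 9.0% in DINAMO) already miss the 7.0% and 6.5% targets, so NCF response does not change for them. In OC, however, their value is set to missing.
- The Week 26 cut-off for rescue is not settled in the visible text. Protocol 7.3 censors at the first extension dose, but the SAP 6.7 visit window can run to Day 210. If the window end governed, rescue starts within it would count as failures anyway and the Visit 5 shift would not matter.
- Protocol 3.2 expects virtually all Mono patients who miss glycaemic goals to need rescue and be counted as failures, so how false such a failure is can be debated. The SAP definition still turns on the date.

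A reader might infer that the rule does misclassify failures, or that it undermines the main trial result. The documents support neither: the first needs partial dates near a boundary and no rule in 7.6.1, and SAP 7.4.1.1 keeps HbA1c values after rescue in the DINAMO primary analysis.

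**Conclusion.** The point holds as a small, correctable gap. The visible SAP states a date rule that, applied literally, can place a rescue start on the wrong side of first dose or Visit 5. It can affect the Mono failure endpoint, Mono time to failure and the data sets that depend on rescue timing (OC, OC-LOCF, NCF). The Mono endpoint is exploratory, with no hypothesis test planned. The DINAMO primary analysis is unaffected.

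The number of patients affected is unknown. The consequence of one is known: about 17 points in an arm's failure rate, enough to move zero into or out of the tabulated interval. The conclusion assumes that 7.6.1 has no overriding date rule, that rescue dates follow the concomitant-therapy rule, and that the Visit 5 dose is the Week 26 cut-off.

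**What to change.** In SAP 6.6.3, for antidiabetic therapies, set the imputed start no earlier than the day after the last visit at which concomitant therapy was reviewed and the drug was absent. Also set it no earlier than first study dose, unless the drug was recorded as ongoing before Day 1. Visits 2 and 5 are both review visits, so this covers both boundaries. If 7.6.1 already does this, a cross-reference in 6.6.3 is enough.

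For the DINAMO insulin rule, do not let imputed start and stop dates alone classify a course as longer than 21 days. List those courses and review them blinded before database lock.

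The cost is a few sentences in the SAP, slightly more programming with visit dates already in the database, and a short blinded review.
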